Objectives	This is a prospective study to provide access to an investigational device and reagents used for progenitor cell sorting of a stem cell transplant donor graft to determine the ability of CD34+ cell selection and T Cell depletion (using the
Objectives	CliniMACS [®] device as the sole GvHD prophylaxis) to prevent severe (grade III-IV) acute GvHD in recipients of mismatched related or unrelated donor hematopoietic stem cell transplants or with borderline organ function who might not endure the often toxic side-effects of traditional post-HSCT immunosuppressive therapy.
Primary Endpoint(s)	The primary endpoint of the study is the incidence of severe (grade III/IV) acute GvHD occurring by Day +100 after transplant.
Secondary Endpoint(s)	Outcomes measures for the secondary endpoints will include: Engraftment: The incidence of primary graft failure and graft rejection will be determined. Chimerism at Day 100: The percentage of donor cells will be reported for all evaluable (without disease progression) patients. Immune recovery: The time to CD4 count >100 and > 200 and PHA≥ 10% and 30% will be calculated. Severe toxicities: The incidence of severe toxicities will be determined. This will include grade 3/4 stem cell product infusion-related toxicity. Post-transplant infections (bacterial, viral and fungal): Post-transplant infections will be described by incidence and type. Post-transplant lymphoproliferative disease (PTLD): The incidence of PTLD will be calculated. Transplant-related mortality (TRM): The incidence of TRM will be calculated at Day 100 after transplant and at one year. Disease-free survival. Overall survival: Overall survival will be estimated using the Kaplan-Meier method. Device (CliniMACS®) performance parameters: The parameters will be summarized for all products that are processed and median and ranges will be determined.
Study Design	Participants will be enrolled with alternative (mismatched/haplocompatible) related/unrelated donors or matched related/unrelated donors for an initial HSCT.
Study Centers	This is a Stanford University, Principle Investigator (PI) initiated protocol conducted at LPCH and Stanford Hospital and Clinics.
Duration of Study per Subject	Individual participants will be followed for outcomes related to the experimental device including acute and chronic GvHD and engraftment for a minimum of one year. Subsequent follow-up care will follow the standard for all transplant patients.

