The stopping rule for graft failure yields the probability of stopping the trial of 0.05 if the rate of graft failure is 0.1. The probability of stopping the trial is 0.41 if the graft failure rate is 0.2, 0.82 if the graft failure rate is 0.3, and 0.96 if the graft failure rate is 0.4. These probabilities were calculated based on the binomial distribution.

If the study reaches a stopping boundary, the study will be suspended. Proper use of the stopping rule table will be ensured by the Study Investigator.

Stopping rule for Grade \geq IV toxicity: If any patient develops grade \geq IV acute GvHD, grade \geq IV infection, or any unexpected grade \geq IV toxicity by 4 weeks post-transplant, the protocol will be halted and the processing re-evaluated before

	proceeding.
	Conditions for individual patient termination: Disease progression Need for exclusionary concurrent treatment (per PI discretion) Withdrawal of informed consent Protocol non-compliance
	The PI, through the reports from the Stem Cell Laboratory, will also monitor system performance based on: Cellular composition of final product Yield (% recovery) of CD34+ cells from the starting product CD3+ cell reduction Sterility Purity
Sample Size	The study will enroll 30 transplant recipients at Stanford.
Statistical Methodology	Statistical analysis results will be reported using summary tables, figures, and data listings. Continuous variables will be summarized using the mean, standard deviation, median, minimum, and maximum. Categorical variables will be summarized by numbers and percentages of subjects in corresponding categories. All raw data obtained from the case report form (CRF) and any derived data will be summarized and included in data listings. Missing data will not be imputed.

List of Abbreviations and Definition of Terms

List of Abbreviations	List of Appreviations and Definition of Terms
AE	Adverse event
AdV	Adenovirus
aGvHD	Acute Graft-versus-Host Disease
ALL	Acute Lymphoblastic Leukemia
Allo	Allogeneic
AML	Acute Myelogenous Leukemia
ANC	Absolute Neutrophil Count
ВМ	Bone marrow
BM bx.	Bone marrow biopsy
ВМІ	Body mass index
BMT	Bone Marrow Transplant
BP	Blood pressure
BSA	Body surface area
°С	Degrees Celsius
СВ	Cord blood
CBC	Complete blood count
CD	Cluster of Differentiation
CFR	Code of Federal Regulations
cGvHD	Chronic Graft-versus-Host Disease
CIBMTR	Center for International Blood and Marrow Transplant Research
CML	Chronic Myelogenous Leukemia
CMV	Cytomegalovirus

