1.0 OBJECTIVES

A major issue in alternative donor (mismatched related and unrelated donor) transplantation is the development of graft-versus-host disease (GvHD). For those who cannot receive post-transplant immunosuppressive therapy, any form of graft versus host disease, even with a matched related or unrelated donor can also be a complication. Several clinical trials have shown that the use of T cell-depleted peripheral blood stem cells (PBSC) reduces GvHD in hematopoietic stem cell transplants (HSCT). By using a purified stem cell graft, there is a reduced risk of post-transplant graft versus host disease in patients who have a mismatched donor or cannot receive post-transplant immunosuppression.

This is a prospective study to provide access to an investigational device and reagents used for progenitor cell sorting. The hypothesis is that the CliniMACS® System will allow for a manipulated graft – with augmented CD34+ cells and T cell-depleted numbers --- in a ratio that will prevent severe (grade III/IV) acute GvHD (as defined on appendix C) without the use of prophylactic post-transplant immunosuppression. The incidence of grade III/IV acute GVHD is predicted to be lesser than 10% based on similar ongoing trials (17).

The objective is to manipulate (alter the ratio) specific cells in the donor graft to determine the ability of augmented CD34+ cells and T cell-depleted products to prevent severe (grade III/IV) acute GvHD in recipients of mismatched related donor hematopoietic stem cell transplants as well as to candidates of allogeneic (allo) transplant with borderline organ function -- who might not endure the often toxic side- effects of traditional post-HSCT immunosuppressive therapy.

The patients will receive conditioning therapy based on their diagnosis and per instructional guidelines for treating the disease. The transplant recipients will be followed for one year post- transplant for the development of GvHD, engraftment, post-transplant infections, disease relapse, and overall survival.

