3.4 Study Timeline

There will be no primary completion timeline to this study since the goal isto care for all HSCT recipients that need manipulated transplant graft. Subjects will continue to be followed on study until death or per institutional guidelines, whichever is longer.

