4.3 Criteria for Removal from Study

Conditions for individual patient termination:

- Disease progression
- Need for exclusionary concurrent treatment (per PI discretion)
- Withdrawal of informed consent
- Protocol non-compliance

The Principal Investigator may terminate the study for any of the following reasons:

- Significant toxicities related to the product graft
- If it becomes clear that the study treatment is less effective than other available treatments.

4.4 Duration of Participation in the Study and Follow-up.

Patients will remain in the hospital until there is evidence of engraftment of donor cells as well as recovery from the side effects of transplant conditioning. When the patient has engrafted and meets institutional hospital discharge criteria, they will be discharged from the inpatient facility. Patients will be followed as outpatients at regular intervals in the Bass Center Outpatient Center in the Stem Cell Transplant Clinic. Duration of participation and follow up in study will conclude at day 100 post-transplant.

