10 MEASUREMENT

10.1 Primary and Secondary Outcome measures

The primary outcome will be severe (grade III/IV) acute graft-versus-host disease.

Secondary outcomes will be engraftment date (ANC>500 for 3 consecutive days, and >80% donor cells in blood), graft failure and graft rejection, immune recovery, infection, CMV infection and disease, EBV-related PTLD transplant-related toxicity and mortality, transplant-related mortality, grade 3/4 stem cell product infusion-related toxicity, relapse, DFS, OS.

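### Disease progression is a ground for removal from study, which conflicts with the follow-up promised for overall survival; if removal ends observation, one-year OS will probably read too high

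*Combined protocol and SAP*

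**What the plan says.** **Removal.** The synopsis, under Discontinuation Criteria (Safety Considerations), has "Conditions for individual patient termination: Disease progression", followed by exclusionary concurrent treatment, withdrawal of consent and protocol non-compliance. Section 4.3, headed "Criteria for Removal from Study", gives the same four items.

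**Endpoints.** In the synopsis, "Overall survival will be estimated using the Kaplan-Meier method". For transplant-related mortality (TRM), "The incidence of TRM will be calculated at Day 100 after transplant and at one year". Section 10.1 ends its list of secondary outcomes with "grade 3/4 stem cell product infusion-related toxicity, relapse, DFS, OS".

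**Follow-up.** There are three versions:
- Section 1.0 follows recipients for one year for GvHD, "engraftment, post-transplant infections, disease relapse, and overall survival". The synopsis entry on duration per subject also sets a one-year minimum.
- Section 3.4: "Subjects will continue to be followed on study until death or per institutional guidelines, whichever is longer".
- Section 4.4, directly after the removal criteria, ends participation and follow-up at Day 100.

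No section says whether a patient who meets a termination condition is still followed for vital status. Neither the synopsis methodology nor section 12 gives a censoring rule for OS.

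**The concern.** A patient cannot be removed from the study at relapse and also be followed on study until death. If staff treat section 4.3 as the end of observation, a relapsed patient's OS time stops at relapse, just when the risk of death is likely to rise. That censoring is informative. The Kaplan-Meier curve then describes death without relapse rather than survival, and cannot fairly be set beside the survival figures that the protocol cites (64% predicted at two years in section 2.1; 70 to 75% in section 2.4). Follow-up that was never collected cannot be recovered by a later choice of analysis.

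A patient removed before Day +100 may also drop out of the primary acute GvHD assessment, in a study of only 30 recipients. The documents do not allow that loss to be quantified.

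**Working it through.** The plan states no figure for this bias, so there is nothing to reproduce. The check asks how far one-year OS would move if every relapsed patient were censored at relapse.

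**Inputs from the retrospective US series in section 2.1.** Four patients relapsed: 4/18 = 22% of all patients, or 4/13 = 31% of those at risk. One-year TRM was 19%. Median follow-up was 31 months (range 7 months to 7 years).

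**Assumptions.** Hazards are constant. Annual mortality after relapse, q, is not in the documents; 50, 70 and 90% are used, with 25% as a low case.

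**Formulas.** Let r be the relapse hazard, d the hazard of death without relapse, a = r + d, and m = −ln(1 − q), all per year.
- Cumulative relapse by time t: (r/a)(1 − e^(−at)). TRM has d in place of r.
- OS censored at relapse: e^(−dt).
- OS with deaths after relapse counted: e^(−at) + r(e^(−mt) − e^(−at))/(a − m).

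**Worked case: 22% relapse by 31 months, 19% TRM by one year.** Solving gives r = 0.1303 and d = 0.2258, so a = 0.3561.
- TRM at one year: 0.634 × (1 − 0.700) = 0.19. Relapse at 31 months: 0.366 × (1 − 0.399) = 0.22. Both match the inputs.
- Censored OS at one year: e^(−0.2258) = 79.8%.
- True OS at q = 90% (m = 2.303): 0.700 + 0.1303 × (0.100 − 0.700)/(0.356 − 2.303) = 74.1%. The gap is 5.7 points.

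With 31% by 31 months, r = 0.1995 and d = 0.2342. All one-year results, with q = 50 / 70 / 90%:

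| Relapse assumption | Censored OS | True OS | Gap (points) |
|---|---|---|---|
| 22% by 31 months | 79.8% | 77.8 / 76.2 / 74.1% | 2.0 / 3.6 / 5.7 |
| 31% by 31 months | 79.1% | 76.2 / 73.8 / 70.7% | 2.9 / 5.3 / 8.5 |
| 22% all within one year | 78.3% | 74.4 / 71.1 / 66.8% | 3.9 / 7.2 / 11.5 |
| 31% all within one year | 76.8% | 71.5 / 66.8 / 60.7% | 5.4 / 10.0 / 16.2 |

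For the two 31-month rows, q = 25% gives gaps of 0.3 and 0.4 points. At Day 100 (t = 0.274), q = 50 to 90% gives 0.2 to 0.8 and 0.3 to 1.2 points.

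**Cross-check with other inputs.** The multicentre AML trial in section 2.1 reports 23.7% relapse and TRM below 20% at two years (20% used). With assumed median survival after relapse of 3, 6 and 12 months, one-year OS is 79.3, 82.1 and 84.6%, against 87.7% censored. The gaps are 8.3, 5.6 and 3.0 points, and simulated Kaplan-Meier curves with n = 30 agree. With 31% relapse and 19% TRM both taken at two years, the gaps are 11.2, 7.5 and 4.1 points; a 3-month median means 1 − 2^(−4) = 94% annual mortality, beyond the range in the table.

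**Direction.** It is not automatic. With no deaths after relapse, these two-year inputs make the censored curve about 1 point too low at one year.

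**The case against.** The best defence is that the plan never says OS is censored at relapse. A reader might infer that from 4.3, but sections 1.0 and 3.4 provide for follow-up past progression and section 2.4 puts follow-up on standard CIBMTR forms. If those are followed, this bias does not arise. The rule against imputing missing data does not decide whether vital status is collected. This stands: the defect is a contradiction.

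A reader might also argue that termination can only mean leaving follow-up, because graft processing is finished before infusion. That is not established. Section 5.1 places donor mobilization after enrollment, so a patient could progress before transplant, and section 6.1 stores surplus cells for later use. The list may be meant to stop study procedures. Even so, 4.3 speaks of the study, and nothing keeps terminated patients under observation.

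A third tempting reading is that DFS, relapse and TRM are distorted in the same way. Progression is itself the event for relapse and DFS, so the first event is not lost. For TRM the question is relapse as a competing event, and no bias has been shown.

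Finally, gaps of 4 to 12 or 5 to 16 points need every relapse to fall within one year, which a series with 31-month median follow-up does not support. The 31% rate also applies only to patients with malignancy, whereas this study admits non-malignant disease. One of the four relapsed patients was in remission more than a year later. With 30 patients, the 95% half-width near 75% is 1.96 × √(0.75 × 0.25/30), about 15 points, so the bias would be smaller than the sampling error. Unlike sampling error, though, it would usually run in one direction.

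**Conclusion.** The contradiction is real and should be removed: grounds for removal in the synopsis and 4.3, follow-up for one year or until death in 1.0 and 3.4, and a Day-100 end in 4.4. Whether OS is biased depends on which text is applied. If 4.3 ends observation, one-year OS reads roughly 2 to 9 points too high, given constant hazards, relapses spread over 31 months and 50 to 90% annual mortality after relapse. Earlier relapse makes it larger. At 25% mortality it is under 1 point, and at Day 100 about 1 point or less. The bias falls on OS; possible loss of primary-endpoint data before Day +100 is a further, unquantified risk.

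Severity is moderate. OS is a descriptive secondary endpoint, and no test, threshold or stopping rule uses it.

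**What to change.** Reconcile 4.3, 4.4 and the synopsis discontinuation list with 1.0, 3.4 and the synopsis duration entry, so that one follow-up length applies throughout. Changing 4.3 and the synopsis alone would leave the Day-100 end in 4.4 in conflict.

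Any rule on stopping study procedures is for the sponsor to settle. Separately from it, state that:
- a transplanted patient who meets a termination condition, other than withdrawal of consent for follow-up, stays in data collection for acute GvHD to Day +100 and for relapse, TRM and vital status to at least one year;
- OS is not censored at progression.

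The cost is a wording amendment and slightly more status checks in relapsed patients. Section 2.4 already puts follow-up on standard CIBMTR forms, so the added burden should be small.

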1.0 OBJECTIVES

A major issue in alternative donor (mismatched related and unrelated donor) transplantation is the development of graft-versus-host disease (GvHD). For those who cannot receive post-transplant immunosuppressive therapy, any form of graft versus host disease, even with a matched related or unrelated donor can also be a complication. Several clinical trials have shown that the use of T cell-depleted peripheral blood stem cells (PBSC) reduces GvHD in hematopoietic stem cell transplants (HSCT). By using a purified stem cell graft, there is a reduced risk of post-transplant graft versus host disease in patients who have a mismatched donor or cannot receive post-transplant immunosuppression.

This is a prospective study to provide access to an investigational device and reagents used for progenitor cell sorting. The hypothesis is that the CliniMACS® System will allow for a manipulated graft – with augmented CD34+ cells and T cell-depleted numbers --- in a ratio that will prevent severe (grade III/IV) acute GvHD (as defined on appendix C) without the use of prophylactic post-transplant immunosuppression. The incidence of grade III/IV acute GVHD is predicted to be lesser than 10% based on similar ongoing trials (17).

The objective is to manipulate (alter the ratio) specific cells in the donor graft to determine the ability of augmented CD34+ cells and T cell-depleted products to prevent severe (grade III/IV) acute GvHD in recipients of mismatched related donor hematopoietic stem cell transplants as well as to candidates of allogeneic (allo) transplant with borderline organ function -- who might not endure the often toxic side- effects of traditional post-HSCT immunosuppressive therapy.

The patients will receive conditioning therapy based on their diagnosis and per instructional guidelines for treating the disease. The transplant recipients will be followed for one year post- transplant for the development of GvHD, engraftment, post-transplant infections, disease relapse, and overall survival.

1.1 Primary Objective

To determine the ability of CD34+ cell selection using the CliniMACS® device as the sole GvHD prophylaxis to prevent severe (grade III-IV) acute GVHD in recipients of alternative donors hematopoietic stem cell transplants and/or potential matched-related allogeneic SCT recipients with borderline organ function (who might not tolerate traditional post-HSCT GvHD prophylaxis without increased morbidity).

1.2 Secondary Objectives

Assess the ability of this approach to serve as a platform for strategies to accelerate post- transplant immunological recovery.

Evaluate chimerism at day +100 (from the date of transplant graft infusion), and the rate of engraftment in recipients of CD34+ cell selected, T cell-depleted transplants from mismatched related donors.

Evaluate the rates of post-transplant occurrences, including:

- a) Graft rejection and graft failure
- b) Immune recovery
- c) Transplant-related severe toxicities
- d) Post-transplant infections
- e) CMV infection and disease
- f) EBV-related post-transplant lymphoproliferative disorder (PTLD)
- g) Relapse of malignant-diagnosis
- h) Transplant-related mortality
- i) Disease-free survival (DFS) and overall survival (OS)

Monitor device performance:

- a) Cellular composition of final product
- b) Yield of CD34+ cells
- c) CD3+ cell depletion
- d) Sterility
- e) Purity

2. BACKGROUND

2.1 Previous Studies

Hematopoietic stem cell transplantation (HSCT) is now recognized as an effective form of therapy for an increasing number of malignant and non-malignant disorders. Therefore, extending the donor pool to alternative sources of hematopoietic stem cells (HSCs) that are capable of reconstituting hematopoiesis after intensive myeloablative therapy is an important goal in this field. The preferred donor for an allogeneic HSCT is an HLA identical sibling. However, less than 25% of patients requiring a transplant will have such a donor. Alternative stem cell sources include volunteer matched unrelated donors (URD) and unrelated donor cord blood (CB).(1) For patients lacking either a matched sibling donor or a suitable unrelated donor in a timely fashion, mismatched related donors could be a potential option.

To overcome the lack of suitable donors, transplant centers around the world started using mismatched (haplocompatible or sharing only one of two haplotypes) related donors. In the past, the major challenges have been engraftment, graft-versus-host disease (GvHD), and an increased incidence of infection and disease relapse.

Outcomes have improved markedly in recent years with the availability of cell selection devices that allow the administration of a large number of stem cells with a low dose of T cells and the development of more intensely immunosuppressive conditioning regimens. In an effort to reduce the high risk of fatal GvHD associated with these mismatched donors, the stem cells need to be processed to significantly reduce the number of donor T cells present in the graft. CD34 is a receptor that is expressed on early hematopoietic stem cells (HSC). Monoclonal antibodies are available that efficiently bind to the CD34 antigen. Studies have shown that positive selection of CD34+ marrow or blood cells results in a significant (> 4 log) depletion of T cells from the preparation (8-10). This approach is less time-consuming and may be more efficient than earlier approaches because it specifically targets the HSC. A cell separation system for clinical use is available for evaluation in the US after extensive use in Europe (11,12). The Miltenyi Biotec Inc. CliniMACS® CD34+ Reagent System has the advantages of the best T cell depletion efficiency achievable and a very high efficiency of CD34+ cell recovery so that fewer apheresis are necessary. The CliniMACS® device uses a sterile, closed magnetic sorting system to isolate CD34+ stem cells.

The bone marrow or peripheral blood stem cell product obtained from the donor is incubated with a murine anti-CD34 monoclonal antibody conjugated to small super- paramagnetic beads composed of iron dextran (commercially available to treat iron deficiency). The murine antibody has been used in clinical trials in humans. The dose administered to the transplant after processing is 100 times lower than therapeutic levels. Following incubation, unbound reagent is removed by washing the cell product and the product loaded onto the CliniMACS®. The cells are passed through a strong magnetic field applied to the CliniMACS® column and the CD34+ cells retained on the column while other cells (T, B, and NK cells, monocytes, and neutrophils) pass through into a waste bag. The magnet is withdrawn and the CD34+ cells eluted from the demagnetized column into a blood transfer pack for final formulation prior to release for infusion.

It has been well established that allogeneic peripheral blood stem cells (PBSC) recruited into the blood by administering G-CSF can successfully and durably engraft in both matched (13,14) or mismatched (15,16) transplant settings. PBSC recruited with cytokines generally engraft earlier and contain a larger number of HSC compared to marrow HSC (14,15).

Much of the work that has been done with this approach has been reported by a group in Perugia, Italy. They used the CliniMACS® device to lower the T cell content of the donor PBSC to a median of 1 x 10^4 /kg (range 0.04 – 3 x 10^4 /kg). Ninety-one percent of patients had primary engraftment. Six of seven patients who did not have primary engraftment were successfully engrafted after a second transplant, making the overall engraftment rate 99%. Grade III-IV acute GvHD occurred in 2% of patients. The transplant-related mortality was 37%, with the majority of deaths due to infection (bacterial, viral, and fungal). Relapse occurred in 16% of 66 patients who were in remission at the time of transplant. The two-year EFS for patients in remission was 48% for AML and 46% for ALL (17).

The results of haplocompatible transplantation in children have been encouraging. Handgretinger reported a 46%

two years EFS in patients with ALL in CR1-3 (18) Ortin et al. reported 75% EFS of patients with ALL in CR2/3 with median follow-up of 18 months (range 6-29) (19). The international experience was reviewed at a conference in Naples in 2004. Lang updated the Tubingen, Germany experience when he reported a 44% 2 years EFS for 21 children with ALL in CR1-3 (20)

Advantages of haplocompatible transplantation are rapid engraftment and the very low incidence of severe acute GVHD. Ortin et al. reported a median time to ANC > 500 and to platelet count > 50,000 of 12 and 20 days, respectively, with the incidence of grade III/IV acute GvHD being 5% (19). Lang reported a 1% incidence of grade III/IV acute GvHD (21).

In a retrospective review of the experience of 3 investigators in the U.S. (Cowan, Gilman, Sleight) with alternative (haplocompatible) donor transplant using CD34+ cell selection for T cell depletion, 13/18 (72%) were surviving with follow-up of 7 months – 7 years (median 31 months)(22). The median patient age was 8 years (range 1-20). Patient with malignancy (n=13) included: AML - CR1 (primaryinduction failure, failed cord blood transplant) [1], CR2 [3]; MDS - RA/RARS [2], RAEB [2]AM (and Fanconi anemia, FA) [1]; CML - CP2 [1]; ALL - CR3 [2]; NHL - CR2 [1]. Patients with non-malignant (n=5) disease included severe aplastic anemia (1 with prior bone marrow transplant three years earlier) [4] and Wiskott-Aldrich syndrome [1].

Fourteen donors were a 3/6 HLA match and 5 were a 4/6 match (one patient had two transplants using different donors). A CD34-positive selection device – Miltenyi CliniMACS $^{\otimes}$ (15), Isolex (3) – was used to select stem cells and deplete T lymphocytes. Patients received a median of 18 x 10 6 CD34+ (stem) cells/kg (range 6-28) and 3 x 10 4 CD3+ (T) cells/kg (range 0.3-11).

Sustained primary engraftment occurred in 15/18 (83%) patients. Primary graft failure occurred in one patient. Two patients had immunological rejection following HHV-6 reactivation. They both engrafted after a second transplant; therefore the overall engraftment rate was 94%. The median time to an ANC >0.5 x 10⁹/L was 12 days (range 9-21). Platelet recovery occurred in 16/18 at a median of 17 days (range 9-22). Grade II acute GvHD was seen in 4/17 patients (24%). Grade III-IV acute GvHD was seen in 1 pt. (6%) with overlap syndrome (acute + chronic GvHD) associated with HHV-6 reactivation. Nine patients received DLI and/or stem cell boosts (boosts for graft rejection); 4 had grade II GvHD (3/4 had a history of acute GvHD) and none had grade III-IV GvHD. After DLI and/or stem cell boost, two patients developed extensive chronic GvHD and one developed overlap syndrome. The day 100 mortality and one year transplant-related mortality were 11% and 19%, respectively. Four patients (of 13 at risk, 31%) have relapsed; 1 patient with cytogenetic relapse is in CR > 1 year later. The 2 year predicted survival is 64% (60% for 13 patients with malignant disease and 75% for 5 patients with non- malignant disease).

Infections were common. All patients were at risk for CMV reactivation. Seven patients (39%) reactivated CMV. All cases were responsive to anti-viral therapy and/or DLI. No CMV disease was seen. Seven patients had adenovirus reactivation and six had HHV-6 reactivation. EBV reactivation occurred in 5/18 (28%) patients, three of whom manifested signs of post-transplant lymphoproliferative disorder.

Patients received a median of 3×10^4 CD3+ cells/kg at the time of transplant. Some patients received additional donor T cells (DLI) for viral reactivation. At three months post-transplant, only 4 of the 15 evaluable patients had a CD4 count > 100. By nine months post-transplant, 10 of the 13 evaluable patients had a CD4 count > 200.

There is an ongoing study at the University of California, San Francisco Medical Center of a prospective trial of CD34+ selected (with the CliniMACS® device) PBSC from mismatched related donors (protocol CC# 01151). Patients received a conditioning regimen including TBI 1200 cGy, thiotepa, fludarabine, and rabbit-ATG (3.5 mg/kg). Patients received a fixed T cell dose of 3 x 10⁴/kg at the time of transplant. Seventeen evaluable patients have been reported with the following diagnoses: ALL (3), AML (6), biphenotypic leukemia (1), CML (1), MDS (1), aplastic anemia (2), congenital amegakaryocytic thrombocytopenia (1) combined immunodeficiency (1), and hemophagocytic lymphohistiocytosis (1).

Twelve of the 17 (65%) were alive and well as of 2010, with follow-up ranging from 3 months to 6.5 years (median follow-up 2.5 years). Survivors include 7/12 (58%) with malignant disease and 5/5 (100%) with non-malignant disease. One patient died at 7 months after transplant due to parainfluenza and Paecilomyces infections and

[figure not shown]
another died at 23 months after transplant due to disseminated Mucor infection, a fungus from the class of Zygomycetes. There was no severe (grade III/IV) acute GvHD. Only 3/17 (18%) of patients achieved > 100 CD4+ T cells/uL by 100 days after transplant and 3/4 of these patients either had received donor T cell infusion for serious viral infections prior to 100 days or had GvHD (in which case the T cells probably represented those causing the GvHD and not providing protection against infection).

A variety of genetic diseases of lymphohematopoiesis have been effectively treated and either cured or ameliorated by allogeneic HSCT from an HLA-matched histocompatible healthy sibling [45, 46]. The conditioning regimen of myeloablative high dose Busulfan along with immunoablative high-dose cyclophosphamide (BU- CY) ± antithymocyte globulin (ATG) was developed in the 1980's after important clinical studies were conducted to better understand the prerequisites for replacement of hematopoietic stem cells (HSC) carrying deleterious mutations with those derived from matched healthy donors [46]. These studies established that, in the setting of histocompatible transplant, ablation of host hematopoietic stem cells with high-dose BU (16 mg/kg, 600 mg/m2, or 640 mg/m2) and of host immunity with CY ± ATG allowed durable engraftment of donor HSCs.

[figure not shown]
Since most patients lack a histocompatible sibling donor, a major challenge in the treatment of the genetic lymphohematological disorders is the development of HSCT regimens that result in high levels of engraftment while avoiding regimen-related toxicity and GVHD. Higher risks of graft rejection and GVHD with the use of alternative donors, including unrelated donors (URD), mismatched related donors (mMRD), umbilical cord blood units, and haplo-identical donors, makes these transplants high risk and are associated with high rates of TRM as well. Consequently, the results of HSCT for patients with genetic disorders, using alternative donors has been both limited and suboptimal [47-54].

Given the especially increased risk of rejection with haploidentical transplants in patients with non-malignant disorders [52,54], we are proposing the use of additional immunosuppression to the standard back-bone of Busulfan/cyclophosphamide/anti- thymocyte globulin, by adding Fludarabine.

Miltenyi supported a Phase II multi-center clinical trial sponsored by the BMT CTN (BB-IDE 11965) which enrolled 47 AML patients from October 2005-December 2008 Evaluated the use of the CliniMACS® CD34 Reagent System for selecting CD34+ cells from HLA-matched related donors for allogeneic stem cell transplantation after myeloablative therapy in patients with Acute Myeloid Leukemia (AML) in 1st or 2nd CR, without additional GvHD prophylaxis

Post processing outcomes in all centers were able to process grafts that met the study criteria.

[figure not shown]
- All patients received the minimum CD34+ dose (> 2.0 x 10⁶ cells/kg)
- 84.1% of patients received > 5 x 10⁶ CD34+ cells/kg

Final Cellular Product Summary

Parameter	Result
Median CD34⁺ dose	7.92 x 10 ⁶ /kg
Range	2.4 - 30.3 x 10 ⁶ /kg
Median CD3+ dose	0.7 x 10 ⁴ /kg
Range	0.1 – 8.3 x 10 ⁴ /kg
Median Log ₁₀ TCD	4.9 logs
Range	3.2 – 5.9 logs

- All Gram stains/14 day cultures were negative
- All endotoxin < 5.0 EU/kg
- No significant infusion related toxicities observed

Primary Endpoint 6 Month Disease-Free Survival of >75%

The BMT CTN 0303 conclusions was that HCT following myeloablative preparative regimen for patients with AML in CR1 or CR2 can be performed in a multicenter setting using the CliniMACS® CD34 Reagent System without additional post-transplant pharmacologic GvHD prophylaxis

All 1° and most 2° endpoints were met, demonstrating:

- 81.8% Disease-Free Survival 6 months post TX
- No primary graft failure; consistent neutrophil and platelet engraftment
- Acute GvHD grades II-III <23%. No Grade IV aGvHD
- Chronic GvHD at 2 years 19%; extensive 6.8%
- TRM <20% at 2 years
- Overall risk of relapse was low at 23.7% at 2 years

The CliniMACS® CD34 Reagent System consistently produced a graft with > 2×10^6 CD34+ cells/kg and < 1×10^5 CD3+ cells/kg with no reported device related toxicities.

In January, 2014, the CliniMACS[®] CD34 Reagent System received FDA approval as a Humanitarian Use Device for processing hematopoietic progenitor cells collected by apheresis from an allogeneic, HLA-identical, sibling donor to obtain a CD34+ cell-enriched population for hematopoietic reconstitution following a myeloablative preparative regimen without the need for additional GvHD prophylaxis in acute myeloid leukemia.(44)

In summary, the use of CD34+ selected PBSC and manipulated bone marrow grafts without post-transplant GvHD prophylaxis for children was associated with rapid engraftment, low 100-day mortality, very low incidence of severe GvHD, and excellent survival. The overall survival compares favorably with matched-related and URD HSCT. Immune reconstitution was slow and post-transplant infections contributed to morbidity and mortality.

